3.10. Dose Modifications for Trametinib and supportive care

3.10.1. Liver Chemistry Stopping Criteria

Liver chemistry threshold stopping criteria have been designed to assure subject safety and to evaluate liver event etiology during administration of study treatment(s) and the follow-up period. Study treatment(s) will be stopped if any of the following liver chemistry stopping criteria is/are met:

1. Alanine aminotransferase (ALT) ≥ 3 X (times) upper limit of normal (ULN) and bilirubin ≥ 2 Xs ULN (or ALT ≥ 3 X ULN and international normalization ratio [INR] > 1.5)

NOTE: Serum bilirubin fractionation should be performed if testing is available. If fractionation is unavailable, urinary bilirubin is to be measured via dipstick (a measurement of direct bilirubin, which would suggest liver injury).

2. ALT ≥ 5 X ULN.
3. ALT ≥ 3 X ULN if associated with the appearance or worsening of rash or hepatitis symptoms (fatigue, nausea, vomiting, right upper quadrant pain or tenderness, or jaundice) or hypersensitivity (such as fever, rash or eosinophilia).
4. ALT ≥ 3 X ULN persists for ≥ 4 weeks.
5. ALT ≥ 3 X ULN and cannot be monitored weekly for 4 weeks.

Subjects with ALT ≥ 3 X ULN **and** < 5 Xs ULN **and** bilirubin < 2 X ULN, who do not exhibit hepatitis symptoms or rash, can continue study treatment(s) as long as they can be monitored weekly for 4 weeks. As with other causes of dose holding, discussion with the medical monitor is required if trametinib is held for > 21 days. See following section for details on weekly follow-up procedures for these subjects.

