3.10.1.1. Liver Chemistry Follow-up Procedures

Refer to the diagram in Appendix 5 for a visual presentation of the procedures listed below.

The procedures listed below are to be followed if a subject meets the liver chemistry stopping criteria defined in Section 3.10.1:

- Immediately and permanently withdraw the subject from study treatment.
- Notify the Medical Monitor within 24 hours of learning of the abnormality to confirm the subject's study treatment(s) cessation and follow-up.
- Complete the "Safety Follow-Up Procedures" listed below.
- Complete the liver event electronic case report forms (eCRFs). If the event also meets the criteria of a serious adverse event (SAE) (see Section 8.2), the SAE data collection tool will be completed separately with the relevant details.
- Upon completion of the safety follow-up permanently withdraw the subject from the study and do not rechallenge with study treatment(s).

CONFIDENTIAL

Safety Follow-Up Procedures for subjects with ALT ≥ 3 times ULN:

- Monitor subjects **weekly** until liver chemistries (ALT, aspartate aminotransferase [AST], alkaline phosphatase [ALP], and bilirubin) resolve, stabilize or return to within baseline values.

Safety Follow-Up Procedures for subjects with ALT ≥ 3 times ULN and bilirubin ≥ 2 times ULN (or ALT ≥ 3 times ULN and INR > 1.5):

- **This event is considered an SAE** (see Section 8.2). Serum bilirubin fractionation should be performed if testing is available. If fractionation is unavailable, urinary bilirubin is to be measured via dipstick (a measurement of direct bilirubin, which would suggest liver injury).
- Make every reasonable attempt to have subjects return to the clinic within 24 hours for repeat liver chemistries, additional testing, and close monitoring (with specialist or hepatology consultation recommended).
- Monitor subjects **twice weekly** until liver chemistries (ALT, AST, alkaline phosphatase, bilirubin) resolve, stabilize or return to within baseline values.

In addition, for all subjects with ALT ≥ 3 times ULN, every attempt must be made to also obtain the following:

- Viral hepatitis serology including:
 - Hepatitis A Immunoglobulin M (IgM) antibody.
 - Hepatitis B surface antigen and Hepatitis B Core Antibody (IgM).
 - Hepatitis C ribonucleic acid (RNA).
 - Cytomegalovirus IgM antibody.
 - Epstein-Barr viral capsid antigen IgM antibody (or if unavailable, obtain heterophile antibody or monospot testing).

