11. Men with a female partner of childbearing potential must have either had a prior vasectomy or agree to use effective contraception as described in Section 11.1.2.
12. An Eastern Cooperative Oncology Group (ECOG) performance status of 0 or 1. Refer to Appendix for details.

CONFIDENTIAL

13. Adequate baseline organ function as defined in Table 13.

CONFIDENTIAL

Table 13 Definitions for Adequate Baseline Organ Function

System	Laboratory Values
Hematologic	
ANC	≥ 1.0 × 10 ⁹ /L
Hemoglobin	≥ 9 g/dL
Platelet count	≥ 75 × 10 ⁹ /L
PT/INR ^a and PTT	≤ 1.3 x ULN
Hepatic	
Albumin	≥ 2.5 g/dL
Total bilirubin	≤ 1.5 x ULN
ALT	≤ 2.5 x ULN
Renal	
Creatinine or	≤ 1.5 ULN
Calculated creatinine clearance ^b	≥50 mL/min
Cardiac	
Left Ventricular Ejection fraction (LVEF)	≥ LLN by ECHO, >50% if not specified

Abbreviations: ALT = alanine transaminase; ANC = absolute neutrophil count; INR = international normalized ratio; LLN = lower limit of normal; PT = prothrombin time; PTT = partial thromboplastin time; ULN = upper limit of normal.

- a. Subjects receiving anticoagulation treatment may be allowed to participate with INR established within the therapeutic range prior to randomization. PT and PTT > 1.3 x ULN are permitted in these subjects.
- b. Calculate creatinine clearance using standard Cockcroft-Gault formula (Appendix). Creatinine clearance must be ≥50 mL/min to be eligible.

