Human Immunodeficiency virus (HIV) ^c			
Hepatitis B (HBsAg)			
Hepatitis C (Hep C antibody -- if second generation Hepatitis C antibody positive, a hepatitis C antibody Chiron RIBA [®] immunoblot assay should be reflexively performed on the same sample to confirm the result)			
Follicle stimulating hormone (FSH) and estradiol (as needed in women of non-child bearing potential only)			
a. Coagulation panel to be done at Screening only			
b. If serum creatinine is > 1.5 mg/dL, creatinine clearance should be calculated using the standard Cockcroft-Gault formula (Appendix)			
c. HIV testing is optional			

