- All events of possible study treatment-induced liver injury with hyperbilirubinemia defined as alanine aminotransferase (ALT) ≥ 3 times upper limit of normal (ULN) **and** bilirubin ≥ 2 times ULN ($>35\%$ direct) (or ALT ≥ 3 times ULN and international normalization ratio (INR) >1.5 , if INR is measured) or termed 'Hy's Law' events (INR measurement is not required and the threshold value stated will not apply to patients receiving anticoagulants).

NOTE: Bilirubin fractionation is performed if testing is available. If testing is not available, record presence of detectable urinary bilirubin on dipstick indicating direct bilirubin elevations and suggesting liver injury. If testing is unavailable and a subject meets the criterion of total bilirubin ≥ 2 times ULN, then the event is still reported as a serious adverse event (SAE). If INR is obtained, include values on the SAE form. INR elevations >1.5 suggest severe liver injury.

- Any new primary cancers
- LVEF that meets stopping criteria (see Section 3.9.1.1)
- Retinal pigment epithelial detachment (RPED) or retinal vein occlusion

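### Liver stopping criterion 1 (Section 3.10.1) applies INR >1.5 to anticoagulated subjects, whom the protocol admits and exempts from that threshold for SAE reporting

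*Combined protocol and SAP*

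**What the plan says.** **Treatment rule.** Criterion 1 in Section 3.10.1 has a bilirubin limb and an INR limb. The INR limb reads "ALT ≥ 3 X ULN and international normalization ratio [INR] > 1.5" and is not qualified. The closing paragraph of the same section covers subjects with ALT from 3 to below 5 x ULN and bilirubin below 2 x ULN. Of these it says that those "who do not exhibit hepatitis symptoms or rash, can continue study treatment(s) as long as they can be monitored weekly for 4 weeks". It does not mention INR.

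**Consequence.** For a subject who meets any stopping criterion, Section 3.10.1.1 says: "Immediately and permanently withdraw the subject from study treatment". It also rules out rechallenge. Its SAE line repeats the combination ("or ALT ≥ 3 times ULN and INR > 1.5"), again without an exemption, and refers to Section 8.2.

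**Eligibility.** Table 13 note a (Section 5.2.1) states: "Subjects receiving anticoagulation treatment may be allowed to participate with INR established within the therapeutic range prior to randomization". It also waives the PT and PTT limit for these subjects. Section 10.2 does not prohibit anticoagulants.

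**Reporting rule.** Section 8.2 says: "INR measurement is not required and the threshold value stated will not apply to patients receiving anticoagulants". Table 18 note c (Section 8.5.1) says the same in substance.

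**The concern.** The protocol recognises that an INR above 1.5 should not be read as a liver signal in a subject on an anticoagulant, and it builds this into the rules for classifying and reporting SAEs. The rule that takes the subject off drug lacks the same clause. A subject whom the protocol knowingly admits can therefore lose trametinib permanently because of an INR that reflects another medicine, at an ALT at which other asymptomatic subjects may stay on treatment.

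There is also an effect on the safety tables. Section 8.3 requires an AE to be recorded for a laboratory result that leads to permanent discontinuation. Such a withdrawal would therefore enter the summary of AEs leading to discontinuation in Section 13.3.2.2.3.

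**Working it through.** The plan gives no figure to reproduce, and no sample size, power or alpha is involved. The check is to apply the rules to two subjects who differ only in anticoagulation.

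**Inputs from the documents.** The stopping criteria and continuation paragraph (3.10.1), the consequences (3.10.1.1), the monitoring rule (9.2) and the restart rules (6.3, 9.3, 9.4, Appendix 5).

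**Assumptions.** The documents give no therapeutic INR range. I take a target of 2.0 to 3.0, and considered 2.0 to 3.5. Every value in either range exceeds 1.5. An anticoagulant that leaves INR at or below 1.5 does not raise the problem. I also assume that an on-treatment INR exists. Table 15 note a says "Coagulation panel to be done at Screening only", while Table 14 allows coagulation tests on treatment when clinically warranted.

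**Both subjects.** ALT from 3 to below 5 x ULN, bilirubin below 2 x ULN, no rash or hepatitis symptoms, able to attend weekly.

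| Rule | On anticoagulant, INR >1.5 | Not on anticoagulant, INR ≤1.5 or not measured |
|---|---|---|
| Criterion 1, bilirubin limb | Not met | Not met |
| Criterion 1, INR limb | **Met** | Not met |
| Criterion 2 (ALT ≥5 x ULN) | Not met | Not met |
| Criterion 3 (symptoms, rash, hypersensitivity) | Not met | Not met |
| Criterion 4 (ALT ≥3 x ULN for ≥4 weeks) | Not yet | Not yet |
| Criterion 5 (weekly monitoring impossible) | Not met | Not met |
| Continuation paragraph | Conditions met | Conditions met |

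**Which rule wins for the first subject?** This subject satisfies both the stop and the continue wording in 3.10.1. Section 9.2 settles it: a subject under monitoring who at any time meets one of criteria 1 to 5 goes to the stopping procedures. Section 3.10.1.1 then requires permanent withdrawal. The second subject continues.

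**Distance from entry.** Table 13 allows ALT up to 2.5 x ULN. From that maximum, the INR limb is reached after a rise of 3.0/2.5 = 1.2, or 20%, if INR is already above 1.5.

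**Can the first subject return to treatment?** The text conflicts. Section 3.10.1.1 rules out rechallenge, and 6.3 says a permanently discontinued subject will not receive the drug again. Yet 9.3, 9.4 and Appendix 5 describe restart with case-by-case approval and fresh consent. Section 9.3 needs compelling benefit and no effective alternative. Section 9.4 needs a clear underlying cause and ALT back below 3 x ULN.

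**SAE line in 3.10.1.1.** It omits the exemption but cites 8.2, which contains it. That is a wording mismatch which the cross-reference can resolve. The stopping criterion has no such cross-reference.

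**The case against.** The best defence is that the case is narrow and the error is safe. It needs an anticoagulated subject, an INR above 1.5 that the protocol does not schedule, ALT in a limited band, normal or mildly raised bilirubin, and no rash or symptoms. Criterion 3 already stops subjects at ALT ≥3 x ULN when rash, fatigue or nausea appears or worsens. Section 1.2.3 reports these in 57%, 26% and 18% of trametinib subjects in the Phase III study, so some would stop whatever the INR. Enrolment is at most 25 per cohort. Stopping too early adds no hepatic risk. All of this stands, and it keeps the point minor.

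A second defence is that the Medical Monitor must be told within 24 hours and would recognise an anticoagulant INR. This does not cure the text. In 3.10.1.1 that contact serves to confirm cessation, Section 3.1 allows no waivers, and Section 14.2 permits deviations only to remove an immediate hazard.

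A reader might also infer more than the documents support:

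- **That the INR limb is defective because no on-treatment INR is required.** Section 8.2 and Table 18 note c make the measurement optional by stated choice, and Table 14 allows coagulation tests as warranted and marks one in the follow-up columns. More INR testing would be a preference, not a correction.
- **That the stopping ALT simply falls from 5 to 3 x ULN.** That comparison uses criterion 2 alone. Criteria 3, 4 and 5 also act at 3 x ULN.
- **That Appendix 5 bars restart.** It lists INR as a risk factor suggesting severe liver injury, to be weighed in a benefit-risk review. Its checklist cut-off is also different (≥1.5).
- **That the primary result is at risk.** A withdrawal before the 28-day confirmation could in principle cost a response, but the documents give no number of anticoagulated subjects from which to size this. The rule of 4 responses in 25 is unchanged.

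**Conclusion.** The point holds as an omission in the treatment rule. For an eligible anticoagulated subject whose INR exceeds 1.5 because of the anticoagulant, criterion 1 together with 9.2 and 3.10.1.1 requires permanent withdrawal where a comparable subject may continue under weekly monitoring. That is at odds with the protocol's own position in 8.2 and Table 18 note c.

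It rests on two assumptions: the anticoagulant takes INR above 1.5, and an on-treatment value is available. No expected count can be given. The case should be uncommon, the error is cautious, and the sample size, error rates and primary test are unaffected. It is a minor correction, but the rule gives a wrong result as written.

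**What to change.** Add to criterion 1 in Section 3.10.1 a clause stating that the INR threshold does not apply to subjects on anticoagulants. For consistency with 8.2, add the same clause to the ALT/INR SAE line in Section 3.10.1.1. Optionally, note in Appendix 5 that an INR raised by an anticoagulant is not a restart risk factor.

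All other stopping limbs, including bilirubin and criteria 2 to 5, continue to protect these subjects. The cost is one existing exemption repeated in two places, plus the optional note. It adds no test or visit and does not change the analysis. The conflict over rechallenge between 3.10.1.1 and 6.3 on one side and 9.3, 9.4 and Appendix 5 on the other is not resolved by this clause and needs its own decision.

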3.10.1.1. Liver Chemistry Follow-up Procedures

Refer to the diagram in Appendix 5 for a visual presentation of the procedures listed below.

The procedures listed below are to be followed if a subject meets the liver chemistry stopping criteria defined in Section 3.10.1:

- Immediately and permanently withdraw the subject from study treatment.
- Notify the Medical Monitor within 24 hours of learning of the abnormality to confirm the subject's study treatment(s) cessation and follow-up.
- Complete the "Safety Follow-Up Procedures" listed below.
- Complete the liver event electronic case report forms (eCRFs). If the event also meets the criteria of a serious adverse event (SAE) (see Section 8.2), the SAE data collection tool will be completed separately with the relevant details.
- Upon completion of the safety follow-up permanently withdraw the subject from the study and do not rechallenge with study treatment(s).

CONFIDENTIAL

Safety Follow-Up Procedures for subjects with ALT ≥ 3 times ULN:

- Monitor subjects **weekly** until liver chemistries (ALT, aspartate aminotransferase [AST], alkaline phosphatase [ALP], and bilirubin) resolve, stabilize or return to within baseline values.

Safety Follow-Up Procedures for subjects with ALT ≥ 3 times ULN and bilirubin ≥ 2 times ULN (or ALT ≥ 3 times ULN and INR > 1.5):

- **This event is considered an SAE** (see Section 8.2). Serum bilirubin fractionation should be performed if testing is available. If fractionation is unavailable, urinary bilirubin is to be measured via dipstick (a measurement of direct bilirubin, which would suggest liver injury).
- Make every reasonable attempt to have subjects return to the clinic within 24 hours for repeat liver chemistries, additional testing, and close monitoring (with specialist or hepatology consultation recommended).
- Monitor subjects **twice weekly** until liver chemistries (ALT, AST, alkaline phosphatase, bilirubin) resolve, stabilize or return to within baseline values.

In addition, for all subjects with ALT ≥ 3 times ULN, every attempt must be made to also obtain the following:

- Viral hepatitis serology including:
 - Hepatitis A Immunoglobulin M (IgM) antibody.
 - Hepatitis B surface antigen and Hepatitis B Core Antibody (IgM).
 - Hepatitis C ribonucleic acid (RNA).
 - Cytomegalovirus IgM antibody.
 - Epstein-Barr viral capsid antigen IgM antibody (or if unavailable, obtain heterophile antibody or monospot testing).
 - Hepatitis E IgM antibody (if subject resides outside the United States (US) or Canada, or has traveled outside US or Canada in past 3 months).
- Serum creatine phosphokinase and lactate dehydrogenase.
- Fractionate bilirubin, if total bilirubin ≥ 2 times ULN.
- Obtain complete blood count with differential to assess eosinophilia
- Record the appearance or worsening of clinical symptoms of hepatitis or hypersensitivity, such as fatigue, nausea, vomiting, right upper quadrant pain or tenderness, fever, rash or eosinophilia, on the AE eCRF.
- Record use of concomitant medication(s), acetaminophen, herbal remedies, other over-the-counter medication(s), or putative hepatotoxins on the Concomitant Medications eCRF.
- Record alcohol use on the Liver Events eCRF.

CONFIDENTIAL

The following are required for subjects with ALT ≥ 3 times ULN **and** bilirubin ≥ 2 times ULN but are optional for other abnormal liver chemistries:

- Anti-nuclear antibody, anti-smooth muscle antibody, and Type 1 anti-liver kidney microsomal antibodies.
- Liver imaging (ultrasound, magnetic resonance imaging [MRI] or computed tomography [CT] scan) to evaluate liver disease.
- Liver Imaging and/or Liver Biopsy eCRFs are also to be completed if these tests are performed.
- Serum acetaminophen adduct HPLC assay (quantifies potential acetaminophen contribution to liver injury in subjects with definite or likely acetaminophen use in the preceding week [CTCAE, 2009]).
- Only in those with underlying chronic hepatitis B at study entry (identified by positive hepatitis B surface antigen): quantitative hepatitis B DNA and hepatitis delta antibody. **NOTE:** If hepatitis delta antibody assay cannot be performed, it can be replaced with a PCR of hepatitis D RNA virus (where needed) – as outlined in: <http://www.ncbi.nlm.nih.gov/pmc/articles/PMC1153793>.

3.10.2. Guidelines for Prolonged QTc

Investigators should review concomitant medication usage for those that cause a prolonged QTc. Guidelines for dose modification and stopping criteria due to QTc-prolongation are provided (see Table 9).

Table 9 Withholding and Stopping Criteria for QTc-Prolongation

QTc-Prolongation ^a	Action and Dose Modification

 • QTcB ≥ 501 msec 	
 • Interrupt all study treatments until QTcB prolongation resolves to grade 1 or baseline • Test serum potassium, calcium, phosphorus and magnesium. If abnormal correct per routine clinical practice to within normal limits. • Review concomitant medication usage for a prolonged QTc. • Restart at current dose level^{b,c} • If event recurs, permanently discontinue study treatments

Abbreviations: msec = milliseconds; QTcB = QT interval on electrocardiogram corrected using the Bazett's formula

- a. Based on average QTc value of triplicate ECGs. For example, if an ECG demonstrates a prolonged QT interval, obtain two or more ECGs over a brief period, and then use the averaged QTc values of the three ECGs to determine if study treatments should be interrupted or discontinued.
- b. If the QTc prolongation resolves to grade 1 or baseline, the subject may resume study treatment if the investigator and medical monitor agree that the subject will benefit from further treatment.
- c. If dose is delayed more than 21 days, discussion with the medical monitor is required to resume therapy.

CONFIDENTIAL

3.10.3. Guidelines for Rash

Rash is a frequent AE observed in subjects receiving trametinib (see the Investigator’s Brochures [GlaxoSmithKline, 2012] for more information). Recommendations for supportive care and guidelines for dose modifications for rash are based on experience with other MEK inhibitors and EGFR inhibitors (Balagula 2011; Lacouture 2011) and are provided (see Table 10 and Table 11).

Commented [d1]: Change to Novartis 2016?

The institutional standards for the management of skin-related AEs can differ from these guidelines. In this case, best clinical judgment should be applied and a consultation with the Medical Monitor may be required.

Table 10 Guidelines for Supportive Care of Rash

Type of Care	Action
Prevention/Prophylaxis ^a	
• Avoid unnecessary exposure to sunlight• Apply broad-spectrum sunscreen (containing titanium dioxide or zinc oxide) with a skin protection factor (SPF) ≥ 15 at least twice daily.• Use thick, alcohol-free emollient cream (e.g., glycerine and cetomacrogol cream) on dry areas of the body at least twice daily.• Topical steroids and antibiotics should be applied at least twice daily starting on Day 1 of study treatment, to body areas such as face, chest, and upper back.
• Use mild-strength topical steroid (hydrocortisone 1% cream)or• topical antibiotic (e.g., clindamycin) or oral antibiotics (e.g., doxycycline 100 mg BID, minocycline 100 mg BID)
Symptomatic Care ^b	
• Pruritic lesions: cool compresses and oral antihistamine therapies• Fissuring lesions: Monsel’s solution, silver nitrate, or zinc oxide cream• Desquamation: thick emollients and mild soap• Paronychia: antiseptic bath, local potent corticosteroids in addition to oral antibiotics; if no improvement, consult dermatologist or surgeon• Infected lesions: appropriate bacterial/fungal culture-driven systemic or topical antibiotics

Abbreviations: BID = twice daily; SPF = sun protection factor

- a. Rash prophylaxis is recommended for the first 6 weeks of study treatment
- b. Subjects who develop rash/skin toxicities should be seen by a qualified physician and should receive evaluation for symptomatic/supportive care management

Guidelines for management and dose reduction for rash considered to be related to study treatment are provided (see Table 11).

CONFIDENTIAL

Table 11 Management and Dose Modification Guidelines for Rash

CTCAE Grade	Adverse Event Management	Action and Dose Modification
Grade 1	
 Initiate prophylactic and symptomatic treatment measures^a Use moderate strength topical steroid^b Reassess after 2 weeks 	
 Continue study treatment If rash does not recover to baseline within 2 weeks despite best supportive care, reduce trametinib by one dose level^c
Grade 2	
 Initiate prophylactic and symptomatic treatment measures Use moderate strength topical steroid^b Reassess after 2 weeks 	
 Reduce trametinib by one dose level 
 If rash recovers to \leqgrade 1 within 2 weeks, increase dose to previous dose level If no recovery to \leqgrade 1 within 2 weeks, interrupt study treatment until recovery to \leqgrade 1 Restart trametinib at reduced dose level^c
Grade\geq3	
 Use moderate strength topical steroids^b PLUS oral methyl-prednisolone dose pack Consult dermatologist 	
 Interrupt trametinib until rash recovers to grade \leq1 Restart^c trametinib reduced by one dose level^d If no recovery to grade \leq2 within 4 weeks, permanently discontinue trametinib

Abbreviations: CTCAE = Common Terminology Criteria for Adverse Events

- a. Rash prophylaxis is recommended for the first 6 weeks of study treatment
- b. Moderate-strength topical steroids: hydrocortisone 2.5% cream or fluticasone propionate 0.5% cream
- c. Approval of medical monitor is required to restart study treatment after >21 days of interruption.
- d. Escalation of study treatment to previous dose level may be considered if no rash is evident 4 weeks after restarting study treatment

